## 1.1 Project Summary

Type 1 diabetes (T1D) is one of the most common chronic diseases of childhood. Improving lives of children and families living with T1D is a critical goal with expected benefits for the individual, caregivers, healthcare system and wider society.

Automated insulin delivery via an advanced hybrid closed loop (AHCL) system is accepted as the most effective management strategy, proven in clinical trials and real-world studies, wherein a continuous glucose monitor (CGM) provides glucose information to an insulin pump which can then adjust insulin delivery via an algorithm (housed in an application or in the pump). Due to the established glycaemic benefits, access to AHCL therapy is recommended for all children with T1D according to the latest international guidelines(1).

However, despite national subsidy for CGM, AHCL access in Australia is limited as insulin pumps are primarily self-funded or accessed via health insurance funds or philanthropic programs. This has led to significant inequity in accessing AHCL.

The Department of Endocrinology and Diabetes at Perth Children’s Hospital is implementing a new clinical model of care that will provide early access to AHCL to all children with a new diagnosis of T1D. This study aims to evaluate the impact of the new model of care through a combination of routinely collected clinical information and prospectively collected survey data. Glycaemic control at 6, 12 and 24 months post diagnosis in children with newly diagnosed T1D at Perth Children’s Hospital will be compared to a historical cohort (diagnosed prior to this new model of care). The psychosocial wellbeing of participants will be explored and described through prospectively collected data and cost-effectiveness of this model of care will be evaluated. The overall objective is to comprehensively evaluate a model of care providing early access to AHCL following diagnosis of T1D.

There are no potential ethical concerns in the proposed study.

[figure not shown]
## 2 Rationale / Background

Type 1 diabetes (T1D) is one of the most common chronic diseases of childhood, with an increasing incidence worldwide (2, 3). Despite significant advances in management strategies for T1D, majority of Australian children and adolescents do not currently achieve the recommended glycaemic goals (4). Glycaemic control directly impacts the 16-year mortality gap for youth diagnosed with T1D at <10 years of age (5), and suboptimal control increases the risk of long-term physical (nephropathy, retinopathy, cardiovascular disease) and mental health morbidity. Data from registry studies demonstrate that the trajectory of glucose control in the first 12 months post diagnosis is strongly associated with long-term glucose control (6). By 12 months post diagnosis, HbA1c, a 3-month measure of glucose exposure to the red blood cell and the primary parameter for monitoring long-

term control in T1D, has risen above target goal in the majority (7). Hence, the importance of providing the best therapies in the newly diagnosed period for establishment and maintenance of early tight glucose control is indisputable.

Technological advancement in diabetes therapy has seen the introduction of advanced hybrid closed loop (AHCL) therapy emerge as the strongly recommended therapy for management in youth with T1D in recently published international guidelines (1, 8). In an AHCL system, insulin delivery is automated, relying on glucose levels from a continuous glucose monitor (CGM) communicating with an insulin pump. The insulin pump then adjusts insulin delivery semi-autonomously via a preset algorithm (please refer to Figure 1 below). AHCL has been demonstrated to be safe and effective in improving glucose control in children in both research and real-world settings (9-11). AHCL therapy reduces diabetes burden for children and their caregivers by reducing the risk of hypoglycaemia and daily work related to diabetes care, thus reducing psychological distress (12). In Australia there are currently three commercially available AHCL systems approved by the Therapeutic Goods Administration (TGA); the CamAPS system with the Ypsomed insulin pump paired with Dexcom G6 CGM (approved for youth >1 year of age), the Tandem t-slim insulin pump paired with Dexcom G6 CGM (approved for youth >6 years of age) and the Medtronic 780G insulin pump paired with Guardian G4 glucose sensor (approved for youth >7 years of age). These systems have become increasingly available in Australia since early-2022 and comprise the primary diabetes management system for approximately half of the children cared for with T1D at Perth Children's Hospital (PCH).

**Figure 1**

In Australia, current funding models limit access to these AHCL systems for many children. Insulin pumps may be obtained via high tier private health insurance or self-funding, but the significant cost of ongoing private health insurance and the outright cost of insulin pumps (approximately \$8000) which require replacement every 4 years due to warranty expiry, represent a major barrier for many in regard to accessing insulin pump therapy, and therefore AHCL therapy. Limited philanthropic programs exist in Australia to support those unable to afford pumps (13). The Perth Children's Hospital Foundation (PCHF) Pump Program funded by a PCHF grant has been instrumental in supporting youth in Western Australia to access pump therapy where this would otherwise have been cost-prohibitive for the family (14). However, within these programs, strict criteria apply and limited pumps are available; thus a significant gap remains in accessing AHCL therapy. In direct contrast, the Australian government has subsidised CGM for children living with T1D since 2017, significantly increasing uptake of this technology (15), such that majority of children now use this as their primary glucose monitoring method.

In research settings where hybrid closed loop has been initiated early following diagnosis of T1D, glycaemic control is significantly improved in comparison to the standard practice of multiple daily injections (MDI) (16). Likewise, there is also real-world data both nationally and internationally which show that children who are commenced on AHCL therapy have improved glycemic outcomes (9-11). These positive outcomes have led to the recommendation of AHCL therapy to be offered to all

children with T1D (8). Hence, as a clinical service, we want to offer a service that meets international guidelines, that is AHCL for all children with introduction of this management strategy as early as possible following diagnosis.

Therefore, the PCH Diabetes Service has implemented a model of care aligning with international guidelines to commence AHCL therapy in children following the diagnosis of T1D, alongside initiating ACHL in those with an established diagnosis of T1D. In youth with newly diagnosed T1D cared for within our service, the time to AHCL commencement has reduced from a mean of 9.37 months in 2022 (inclusive of 45 individuals to date) to 3.55 months in 2023 (inclusive of 30 individuals to date). However, given ACHL access is limited to restrictive pathways based on financial status or limited philanthropy, there is a significant gap in equitable access of essential AHCL therapy. This is reflected by the above numbers of those starting AHCL in the newly diagnosed period, as this represents approximately one third of the newly diagnosed T1D cohort in a 12 month period at PCH. Currently, individuals unable to access AHCL are initiated and maintained on MDI with access to a CGM. Hence, in an attempt to improve access, the department has acquired funded support to provide pumps for children who do not have access to pumps through the existing pathways.

The overarching goal of this study is to evaluate the new model of care within the diabetes department at PCH which aims to offer AHCL therapy to **all** children with newly diagnosed T1D, regardless of financial status. AHCL will be offered within 12 weeks following diagnosis of T1D, a time frame in keeping with limited studies in this period, for example the CLOuD trial (16) showing improved outcomes when AHCL was started within 6 weeks from diagnosis, as well as expert input from the Diabetes Clinical Service leads regarding realistic timeframes within current clinical pathways. The combination of a clinical pathway aiming for early initiation of AHCL and equitable technology access for all children is an innovative model of care in T1D. Comprehensive evaluation of the glycaemic outcomes, patient reported outcomes, feasibility and cost-effectiveness of the model are essential and hence are the broad aims of the study.

Real-world evaluation of such models of care represent essential first steps toward collecting the evidence required for improving equitable access to diabetes technology for youth with T1D in both Australia and worldwide.

### 3 Project Aims / Objectives / Hypotheses

#### Specific Aims

1. To determine whether a model of care implementing equitable, early access to AHCL in the first 12 weeks post diagnosis of T1D, is associated with improved glycaemic outcomes, compared to recent historical controls, over the first 24 months post diagnosis.
2. To longitudinally assess disease burden, treatment satisfaction and psychosocial well-being in children and caregivers who are initiated on AHCL early post diagnosis of T1D, over the first 24 months post diagnosis.
3. To evaluate the cost-effectiveness of early, equitable AHCL access as a model of care in comparison to a previous model of care.
4. To investigate the feasibility of commencing AHCL within 12 weeks post diagnosis of T1D, specifically uptake and acceptance of early AHCL therapy and if applicable, the rates and reasons for discontinuation of AHCL.

We hypothesise that the new model of care will result in improved HbA1c at 6, 12 and 24 months post diagnosis of T1D as compared to the historical cohort. Furthermore, we hypothesise potential reduction in psychological distress and disease burden within the new model in comparison to recent historical control. We also hypothesise that the AHCL attrition rates will be low and the model will be cost-effective.

## 4 Project Design

### 4.1 Project Design

This is a hybrid implementation single centre study evaluating the clinical effectiveness and implementation of a new model of care (as outlined in section 4.2), wherein all youth are equitably offered commencement of AHCL within 12 weeks post diagnosis of T1D.

To achieve the project aims:

-HbA1c and CGM metrics will be collected to determine glycaemic outcomes and will be compared to a historical cohort diagnosed under the previous model of care.

-Psychological/person reported outcomes will be collected to evaluate longitudinally the patient experience and potential benefits of the new model for the individual.

-Economic analysis of the new model will be undertaken utilising health utilisation data and specific health service utilisation questionnaires.

-Uptake and if applicable discontinuation rates of AHCL with the new model of care will also be evaluated to investigate the feasibility of the model.

Majority of the data required for analysis in this study is already collected as part of standard clinical care in the PCH Diabetes service. Additional standardised psychological and validated person-reported survey instruments will be collected in order to explore the well-being and quality of life of patients commencing AHCL treatment under the new model.

### 4.2 Model of Care

The PCH Clinical Diabetes Service cares for all children in Western Australia with T1D as all individuals newly diagnosed with T1D are transferred to PCH given it is the only tertiary diabetes paediatric centre in the state.

The routine clinical pathway for individuals following T1D diagnosis at PCH includes:

- Brief admission at diagnosis for insulin injection initiation and basic education
- Multidisciplinary team led intensive outpatient education sessions through the Newly Diagnosed Diabetes Clinic
- Transition from this clinic at approximately 12-16 weeks post diagnosis to age group cohorts for those attending at clinics at PCH or outer metropolitan/regional cohorts for those living within these catchments, for ongoing 3 monthly outpatient follow-up as per gold standard recommendation

Individuals with T1D are offered, encouraged and assisted in considering AHCL systems at all points in the above clinical pathway by their diabetes team, unless a clinical decision made by skilled health care practitioners deems that AHCL is not an appropriate management strategy for an individual (for example; families with significant language barriers may not be able to successfully engage with pump system education which is primarily delivered in English and therefore use of AHCL may be deemed unsafe). The primary pathways for AHCL access as previously outlined are high tier private health insurance (approximately 25% of the total clinic cohort), self-funding, or exploration of eligibility for the philanthropic pathways. For individuals meeting these criteria, the clinical team aids them in navigating pump choice and commencement.

Within this model of care, choice is respected for all individuals in regard to insulin management strategy. Individuals self-funding insulin pumps are offered complete choice in their pump, with AHCL initiated where appropriate. For those accessing pumps via philanthropic pathways, pump choice is dependent on eligibility within the program. Finally, some individuals prefer MDI therapy and will not choose to wear a pump; once again, individual choice is always respected.

In the context of independently sourced funds, AHCL will be now offered to all children with T1D within this model of care. As per current model of care, all children accessing insulin pumps irrespective of the pathway to access it, will have extensive support from their diabetes clinical team in regard to management and ongoing access of pump following the 4-year warranty life of their pump, should they wish to continue with this therapy.

### **4.3 Source and Selection of Participants**

**Contemporary Cohort:** All eligible children and adolescents with newly diagnosed T1D between 1st April 2024 to 31st March 2025 under the care of the diabetes service at PCH will be invited to be recruited in the study. Within this cohort, all eligible patients are to be offered AHCL as per the previously outlined model of care and initiated on AHCL within 12 weeks. Consent for participation in the study will be taken by the research fellow (or in their absence, a member of the research team) who is not involved in routine clinical care of the patient. This will occur during their scheduled Newly Diagnosed Clinic appointments rather than at an additional study visit. It will be made clear to those approached and their families that their routine clinical care will not be impacted by declining study participation.

**Historical Cohort:** The historical comparison cohort will include those diagnosed with T1D between 1st April 2022 to 31st March 2023, prior to the change in model of care. Individuals will be identified from the WA Children's Diabetes Database (WACDD). WACDD is a clinical resource, where routine clinical data is collected, entered and stored (see section 4.7.2 and 8.6 below) for individuals with T1D undergoing clinical care at PCH. Where data relevant to the historical cohort is missing, a study investigator will retrospectively collect this data where able/applicable.

### **4.4 Participant inclusion criteria.**

1. New Diagnosis of T1D between 1st April 2024 and 31st March 2025.
2. Age 1-17.99 years.
3. Willing to complete study questionnaires.

### **4.5 Participant exclusion criteria.**

1. Age <1 year old (no TGA approved AHCL system for this age group).
2. Unwillingness to complete study questionnaires.
3. Does not have at least one caregiver that can read and write English for instruments that are not available in translated versions

### **4.6 Participant withdrawal criteria and procedures specifying (if applicable):**

- (a) when and how to withdraw participants from the project;

Participants may withdraw from the study at any time. This will only impact psychological survey instrument data (as below in section 4.7.2). They will otherwise continue on AHCL and receive standard clinical care as per section 4.2. Participants can withdraw from the study by contacting the research team. Information on how to contact the research team will be provided to the individuals at consent for study inclusion both in verbal and written forms.

(b) the type and timing of the data to be collected for withdrawn participant(s);

All research data for withdrawn participants will be excluded. However, clinical data consented for through WACDD will be used for analysis, unless consent for WACDD is simultaneously withdrawn.

(c) whether and how participants are to be replaced;

Participants will not be replaced.

(d) the follow-up for participants withdrawn from the project.

Participants will continue to receive standard clinical care as per section 4.2. They will continue regular follow up with their diabetes team as per normal standard of care at 3 monthly clinic visits.

## **4.7 Method**

This is a single centre, real-world clinical evaluation of a model of care utilising both longitudinal and retrospective clinical data, prospectively collected patient reported outcome measures and validated psychological surveys.

Consent for participation in the study will be taken by the research fellow who is not involved in routine clinical care of the patient during their scheduled clinical appointments to the hospital. Following consent, the participant will be provided with a unique study number which will be used on data collection instruments in place of identifying information.

### **4.7.1 Clinical Pathway to AHCL therapy**

Per section 4.2, patients with newly diagnosed T1D will progress through the newly diagnosed diabetes model of care. Newly diagnosed T1D patients who meet inclusion criteria will be identified by the clinical and study teams and approached for study inclusion.

AHCL pathways will be explored with each individual per section 4.2. For those who are willing and eligible to start AHCL, provided there are no concerns from the clinical team, every effort will be made to complete pump education modules and start AHCL prior to 12 weeks post diagnosis.

### **4.7.2 Data collection**

#### 4.7.2.1 Routine clinical data collection

The WA Children's Diabetes Database (WACDD) stores clinical data from consenting individuals with T1D receiving care at PCH (see section 8.6 below for further details). This data includes clinical (anthropometric/glycaemic/insulin delivery) and sociodemographic data.

Consent for data sharing and research participation is sought from families at time of initial diagnosis of T1D (HREC Ref 2013051EP). Majority of the data proposed to be collected through this study are routinely collected at diagnosis and 3 monthly clinic visits and stored in WACDD.

Data which is routinely collected at these clinic visits will be exported (clinical data from WACDD, device information/insulin delivery/CGM data from proprietary software) at each of the timepoints below.

Of note while majority of the questionnaires planned for collection in this study are additional for study participants (see additional data collected below), Type 1 Diabetes and Life Measure (T1DAL) (parent, child >8 years) and Problem Areas in Diabetes (PAID) (parent and child versions) are already routinely collected clinical measures, also stored in WACDD.

#### 4.7.2.2 Additional data collected

1. Questionnaires collecting information on general quality of life, sleep quality, anxiety, hypoglycaemia fear and diabetes treatment satisfaction will be additionally collected to address the aims of this study. For the questionnaires not routinely collected at clinic, participants will be emailed a link at the appropriate timepoints to be completed online using REDCap.

2. Parental level of education is not routinely collected at diagnosis presently, however is considered important regarding a participant and their families understanding of diabetes education. It will therefore be collected in addition to the baseline sociodemographic and clinical data which is routinely collected.

As majority of the data is already routinely collected at 3 monthly clinic visits, the burden on participants is minimal. There are no additional visits required for this study outside of routine clinical care, and questionnaire completion can be done at a time and in an environment that is convenient to the participants. This could include either at the clinic appointment while waiting to see their diabetes clinical team members or following the appointment at a time suitable for the individual/caregiver.

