#### 4.7.3 Timeline of data collection:

Timeline outlining when each of the data/questionnaires will be collected is listed in the below table. Of note the data collection may not fall precisely at 3 month time-frames post pump start, but given routine follow-up occurs 3 monthly, would be expected to be at 3 monthly intervals +/- 6 weeks based on when the routine clinical appointment occurs.

Blue shade indicates data that is routinely collected through the PCH diabetes service and green shade indicates additional for this study.

	Baseline/ Consent	Pump start	3m	6m	9m	12m	15m	18m	21m	24m
Consent	X									
Sociodemographic and clinical data	X									
Sociodemographic and clinical data: Parental level of education	X									
Glycaemic measures		X	X	X	X	X	X	X	X	X
Device information/Insulin Delivery		X	X	X	X	X	X	X	X	X
Anthropometric data	X	X	X	X	X	X	X	X	X	X

	Baseline/ Consent	Pump start	3m	6m	9m	12m	15m	18m	21m	24m
Significant clinical events		X	X	X	X	X	X	X	X	X
Health Service utilisation & sick day information		X	X	X	X	X	X	X	X	X
Questionnaires										
T1DAL						X				X
PAID						X				X
GAD7		X				X				X
Pittsburgh Sleep Quality Index		X				X				X
DTSQ (and if participant withdraws with permission)		X				X				X
DTSQ (Change)						X				
Hypoglycaemia Fear Survey						X				X
CHU-9D		X				X				X

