# 8 Data Management, Statistical Analysis and Record Keeping

## 8.1 Statistics and Interim Analysis

The cohort newly diagnosed with T1D in the 12 months following study start (the contemporary cohort) will be compared to a historical control (the cohort newly diagnosed between March 2022 and March 2023). Routine clinical data for both cohorts will be extracted from WACDD. Descriptive statistics (mean/SD, median/IQR, or frequency/% as appropriate) will be presented for key demographic and clinical measures. The 24-month HbA1c in the contemporary cohort will be compared to the historical control through multivariable regression model adjusting for potential imbalances in clinical/sociodemographic characteristics. The adjusted mean difference along with 95% confidence intervals will be calculated. A sensitivity analysis using an inverse probability of treatment weighted regression based on propensity score will also be conducted.

Interim analyses employing similar models examining HbA1c difference between the cohorts at 6 and 12 months will be conducted. Further exploratory analyses presenting mean HbA1c over various clinical factors (e.g. urban/remote postcode/SEIFA, insurance status, age at diagnosis, timing of HCL commencement, etc) will also be conducted. Subanalysis reviewing mean HbA1c on those commencing on AHCL within 12 weeks from diagnosis will similarly be examined.

Device uptake and attrition will be presented as frequencies and proportions along with 95% confidence intervals. Bivariate predictors of device use at uptake will be presented through simple contingency tables of device use by clinical and sociodemographic factors (Age group ( $\leq 12$  years,  $> 12$  years), gender, socioeconomic indices for areas quintile (lowest quintile, other 4 quintiles), DKA at diagnosis).

Simple descriptive statistics (mean/SD, median/IQR, or frequency/%) will be presented for CGM metrics and psychosocial measures at each of the follow-up points for the contemporary cohort. Where appropriate, mixed models or non-parametric Friedman tests will be conducted to assess within person change over time.

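### The first GAD-7, sleep, DTSQ and CHU-9D forms fall at pump start with no requirement to complete them before AHCL begins, so the only possible pre-AHCL reading may mix two treatment states

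*Protocol*

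**What the plan says.** In the table of Protocol section 4.7.3, GAD-7, the Pittsburgh Sleep Quality Index (PSQI), DTSQ and CHU-9D are marked at pump start, 12 months and 24 months. The Baseline/Consent cell is empty for all four. T1DAL, PAID and the Hypoglycaemia Fear Survey are marked only at 12 and 24 months, and DTSQ Change only at 12 months.

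Section 4.7.2.2 describes delivery. For instruments outside routine care, "participants will be emailed a link at the appropriate timepoints to be completed online using REDCap". Completion may take place "either at the clinic appointment while waiting to see their diabetes clinical team members" "or following the appointment at a time suitable for the individual/caregiver". No opening or closing date is given for the link.

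Section 8.1 plans descriptive summaries of the psychosocial measures at each follow-up point in the contemporary cohort. Where appropriate, "mixed models or non-parametric Friedman tests will be conducted to assess within person change over time". CHU-9D has a separate use: it supplies QALYs for the cost-effectiveness analysis, with comparator values taken from the Longitudinal Study of Australian Children (LSAC).

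**The concern.** All patients begin on injections (section 4.2) and are then offered AHCL. Of the three scheduled readings on these instruments, only the pump-start one can describe the child or caregiver before AHCL. If some families answer in the waiting room before the device is started and others answer at home days or weeks later, that reading does not describe one state. The date on which a family opened the link decides which state was recorded.

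DTSQ shows this most clearly. A form completed before the switch rates life on injections, while one completed afterwards rates AHCL. GAD-7 and PSQI are less directly tied to treatment, but they too could move in the first weeks on a new device.

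At stake is the second specific aim, the longitudinal assessment of burden, satisfaction and well-being. For GAD-7, PSQI and DTSQ, the protocol describes no comparison with the historical cohort, so change within person is the main inferential result. Timing is fixed when the data are collected. A later analysis plan can set late forms aside, but it cannot recover a pre-AHCL answer that was never obtained.

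**Working it through.** **The plan's own figure.** The only number for the questionnaire cohort is in section 8.2: at least 80% uptake of 130-150 diagnoses, giving about 105-121 participants. Check: 0.80 × 130 = 104 and 0.80 × 150 = 120, each within one patient of the stated figure. The protocol gives no effect size, SD or power for any questionnaire, so there is no planned change to test against.

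**The sections side by side.**
1. Section 4.7.3: first reading at pump start, none at consent.
2. Section 4.7.2.2: completion before seeing the team is allowed, and so is completion after the appointment without limit.
3. No section makes completion before AHCL use a condition of the pump-start form.
4. Section 8.1: change over time is modelled from these readings.

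Following the protocol exactly can therefore produce first readings from both treatment states.

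**Size of the effect on a change score.** Let f be the share of pump-start forms completed after AHCL began, and g the share of the eventual mean change already present when those forms are completed. Then

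estimated change = true change × (1 − f × g).

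The documents give neither f nor g, so both are assumptions:
- f = 0.25, g = 0.25: 1 − 0.0625 = 0.94 of the true change
- f = 0.5, g = 0.5: 1 − 0.25 = 0.75
- f = 1, g = 0.5: 1 − 0.5 = 0.50
- f = 0.25, g = −0.25 (early weeks temporarily worse): 1 + 0.0625 = 1.06
- f = 1, g = −0.25: 1 + 0.25 = 1.25

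If every form precedes AHCL, f = 0 and the factor is 1. The change from 12 to 24 months does not use the first reading and is unaffected.

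**CHU-9D.** Take assumed true utilities of 0.80 at pump start and 0.85 at 12 and 24 months. By the trapezoid rule, two-year QALYs are (0.80 + 0.85)/2 + (0.85 + 0.85)/2 = 0.825 + 0.850 = 1.675. If half the gain is already in the first value on average, it becomes 0.825, and QALYs are (0.825 + 0.85)/2 + 0.850 = 1.6875, about 1.688. The simple change from pump start falls from 0.050 to 0.025, while the QALYs set against LSAC rise by 0.0125. Under early benefit the error in the QALY total therefore favours the new model of care.

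**The case against.** The strongest defence is that the protocol never calls the pump-start forms a baseline. It has a separate Baseline/Consent column that leaves them out, and the second aim is to follow children who start AHCL, not to contrast before with after. The completion sentence is a general statement about burden that covers every questionnaire at every visit, and it equally allows completion before the team is seen. DTSQ Change at 12 months asks about change in satisfaction directly. The measures are secondary and come from one uncontrolled cohort.

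Much of this stands. The share of late forms is unknown and may be small, and DTSQ Change reduces the dependence on the first DTSQ. But section 8.1 does plan within-person change, and the pump-start reading is its first point. A test of change needs that point to mean the same thing for everyone.

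Several stronger readings are tempting and are not supported:
- **That the benefit of AHCL will be understated.** This needs benefit to appear early. A difficult first few weeks would overstate later improvement, and the documents settle neither. Any single percentage is the product of two assumed quantities.
- **That the CHU-9D benefit is also understated.** Its stated use is QALYs against LSAC, where early benefit in the first value works the other way.
- **That the visit window permits a late pump-start form.** The text that collection "would be expected to be at 3 monthly intervals +/- 6 weeks based on when the routine clinical appointment occurs" concerns the 3-monthly follow-up after pump start and sets no rule for the pump-start form.
- **That families will consent after AHCL has begun.** Of consent, section 4.3 says "This will occur during their scheduled Newly Diagnosed Clinic appointments rather than at an additional study visit", and section 4.2 describes "Transition from this clinic at approximately 12-16 weeks post diagnosis", while section 4.7.1 aims for AHCL before 12 weeks. The overlap makes late consent possible, but it is only an inference: the schedule lists consent ahead of pump start, and section 11 has consent precede the start of the study.

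**Conclusion.** The point holds in a limited form. The protocol fixes the first GAD-7, PSQI, DTSQ and CHU-9D at pump start, allows open-ended completion afterwards, and so does not secure a pre-AHCL reading for the change analyses. The resulting bias is of unknown size and direction. The factors above, 0.50 to 0.94 with early benefit and 1.06 to 1.25 with early worsening, show what assumed values of f and g would do and are not estimates for this study. They also take late completion to be unrelated to how much a family's score will change. For CHU-9D the consequence lies in the first utility value of the QALY calculation. The primary HbA1c comparison does not depend on any of these forms. The change is worth making because it is cheap and the loss cannot be repaired later, but it concerns secondary outcomes only.

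**What to change.** Keep the four forms at the pump-start timepoint. Moving them to consent is not clearly better, because change would then mix adjustment to a new diagnosis with the effect of AHCL.

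- In sections 4.7.2.2 and 4.7.3, state that the pump-start GAD-7, PSQI, DTSQ and CHU-9D are to be completed before first AHCL use, and send the REDCap link ahead of the pump-start appointment. This is a rule about the form only and places no condition on when AHCL starts.
- Record the completion date of each form against the AHCL start date.
- In section 8.1, do not treat forms completed after AHCL start as pre-AHCL values in the change analyses. Alternatively, flag them and exclude them in a sensitivity analysis.
- For CHU-9D, report how many first utility values were obtained after AHCL start.

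The cost is a few sentences of protocol text, an earlier email and one date comparison, with no added visit. The downside is that some late responders lose their pre-AHCL value, so the number contributing to the change analyses may fall below the 105-121 expected to consent.
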